## 6.0 ENDPOINT ASSESSMENT

### 6.1 Primary Endpoint

The primary endpoint will be progression-free survival (PFS) at 3 years. PFS will be measured from start of treatment to time of progression or death from any cause. Progression-free survival will be defined as the absence of either progression or death from any cause. Progression will be evaluated using Cheson 2007 criteria (Revised Response Criteria for Malignant Lymphoma, modified – please see Appendix II). Evidence of clinical progression will be documented by imaging (CT scan or MRI) for patients who have measurable disease. Any patient who receives at least one dose of study treatment will be evaluable for this endpoint.

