## STUDY SCHEMA

Patients must receive at least 4 cycles of induction chemotherapy with or without auto-SCT, including R-CHOP (with or without alternating R-DHAP), R-Hyper-CVAD, or R-bendamustine.

Per Cheson 2007 criteria.

During treatment, 1 cycle = 28 days. Patients will be evaluated (and drug will be dispensed) prior to each cycle for the first 6 months, then every 3 cycles thereafter for the remainder of treatment. See section 4.2 for the provision of 6-month visits after 2 years.

Follow-up schedule for patients off-treatment will be every 3 months up to 2 years post-first dose, then every 6 months up to 4 years post-first dose. Date of progression will be documented as well.

Study Numbers: NU 14H06  
PCI-32765MCL2003Initial version: September 24, 2014  
AMD 11: ver. date 08.06.2022**STUDY SUMMARY**

Title	A Phase II Clinical Trial Evaluating Ibrutinib Maintenance Following Intensive Induction for Patients with Previously Untreated Mantle Cell Lymphoma (MCL)
Version Date	August 8, 2022 (Amendment 11)
Phase/Design	Phase II, single-arm, multicenter, open-label study
Study Center(s)	Lead site: Northwestern University Participating sites: University of Michigan, University of Utah, and Dana Farber d/b/a Massachusetts General Hospital
Objectives	
Primary objective: Determine the 3-year PFS in patients with previously-untreated MCL who achieve response to intensive induction therapy and then receive maintenance Ibrutinib.
 
Secondary objectives:
 
 
• Toxicity
 
• Rates of conversion from PR to CR
 
• Median overall survival at 4 years
 
 
Exploratory objectives: Monitor MRD results by PCR and correlate with PFS and OS.

Sample Size	36 evaluable patients (patients who receive < 1 complete cycle of therapy will not be considered evaluable for efficacy endpoints and will be replaced; we estimate this to represent 3 or fewer subjects)

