Diagnosis and Main Inclusion Criteria	
 
1. Histologically confirmed MCL.
 
2. Disease response (either CR or PR), without known progression, to one (1) prior systemic chemotherapy regimen, with or without consolidative auto SCT. The options are:           
 
a. R-CHOP (with or without cytarabine-containing cycles, including "Nordic" [1] and MCL-NET protocols [2]) with or without auto SCT
 
b. R-Hyper-CVAD with or without auto SCT
 
c. R-Bendamustine with or without auto SCT
 
 
 
3. Prior radiotherapy is permissible.
 
4. Age <math>\geq</math> 18 years.
 
5. ECOG performance status <math>\leq</math> 2.
 

Treatment Plan	Ibrutinib will be given at a fixed dose of 560 mg PO daily throughout the study, to patients who have completed at least 4 cycles of intensive induction chemotherapy (with or without ASCT). The dose is based upon safety and efficacy data. For the purposes of this study, one cycle will be defined as 28 days. This will be continued up to 4 years in the absence of progression of disease, intolerable toxicity, or patient preference (including withdrawal of consent).

Study Numbers: NU 14H06  
PCI-32765MCL2003Initial version: September 24, 2014  
AMD 11: ver. date 08.06.2022

Statistical Methodology	
The primary endpoint is three-year PFS. Our null hypothesis is that ibrutinib maintenance will yield no improvement upon the 60% three-year PFS observed in studies described above. We consider an observed three-year PFS of 80% both feasible and of significant clinical improvement. The study will have 10% Type I error and 90% power to detect an effective treatment using a one-stage design based on the true proportion of patients achieving 3-year PFS is at least 80% versus the null hypothesis that the true complete response rate is at most 60%. Based upon these parameters, our sample size will be 36 evaluable patients. For the final analysis, if 25 or fewer patients are alive and without progression from among all 36 evaluable patients accrued, we will consider this regimen ineffective for this patient population. If, on the other hand, 26 or more patients are alive and without progression, this will be considered sufficient evidence that this treatment may be recommended for further testing in subsequent studies, particularly in a randomized setting.

--------------------------------	--

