### 3.0 SELECTION OF SUBJECTS

The target population for this phase II study is patients with histologically confirmed (previously untreated) mantle cell lymphoma (MCL) who have achieved response (CR or PR) to intensive induction systemic chemotherapy (with or without ASCT). This will be a multicenter trial conducted at Northwestern University. Northwestern University will serve as the lead site and coordinating center for this study. Participating sites will include University of Utah, and Dana Farber d/b/a Massachusetts General Hospital.

A total of 36 *evaluable* subjects will be needed for this trial (defined as having received  $\geq$  1 complete cycle of treatment). Approximately 5 potentially eligible patients are seen per month, and it is anticipated that at least 2 per month will be accrued *once the protocol is open and enrolling at all sites*. Potential patients may be referred to the Principal Investigator (PI) at Northwestern University or to the local PI at each participating site.

Eligibility will be evaluated by the study team according to the following criteria. Eligibility waivers are not permitted. Subjects must meet all of the inclusion and exclusion criteria to be registered to the study. Study treatment may not begin until a subject is registered. Please refer to Section 11.4 for complete instructions regarding registration procedures.

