### 6.2 Secondary Endpoints

#### 6.2.1 Toxicity

All patients who receive at least one dose of ibrutinib will be evaluable for toxicity (including those who are replaced for efficacy endpoints). The study will use the CTCAE version 4.03 (see appendices for link) for reporting of adverse events. The occurrence and severity of each will be recorded.

After the study has been opened for 18 months, patients will be evaluated for an interim safety analysis. The PI along with the Northwestern Lymphoproliferative Disorders disease team and Quality Assurance will assess data to ensure there are no unexpected safety signals that have been observed at this time. See section 10.3.4 for details on the safety analysis.

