#### 6.2.2 Rate of conversion from PR to CR

Progression will be evaluated using Cheson 2007 criteria (Revised Response Criteria for Malignant Lymphoma, modified). Patients must have already achieved either PR or CR during induction chemotherapy prior to enrolling in this study. Patients with measurable disease at time of enrollment will have it followed with imaging. Only patients who had a PR at the time of registration and who complete  $\geq 1$  complete cycle of ibrutinib maintenance therapy will be evaluable for this endpoint. Please refer to appendices for a summary of Cheson criteria.

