## **10.2 Sample Size and Power Calculations**

The primary endpoint is three-year PFS. Our null hypothesis is that ibrutinib maintenance will yield no improvement upon the 60% three-year PFS observed in

studies described above. We consider an observed three-year PFS of 80% both feasible and of significant clinical improvement. The study will have 10% Type I error and 90% power to detect an effective treatment using a one-stage design based on the true proportion of patients achieving 3-year PFS is at least 80% versus the null hypothesis that the true complete response rate is at most 60%.

Based upon these parameters, our sample size will be 36 evaluable patients. For the final analysis, if 25 or fewer patients are alive and without progression from among all 36 evaluable patients accrued, we will consider this regimen ineffective for this patient population. If, on the other hand, 26 or more patients are alive and without progression, this will be considered sufficient evidence that this treatment may be recommended for further testing in subsequent studies, particularly in a randomized setting.

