### **10.3 Planned Analyses**

#### **10.3.1 Primary Objective**

The primary objective will be to determine the progression-free survival (PFS) rate after 2 and 3 years. This will be done in two ways. First, the proportion of patients alive and progression-free at 2 and 3 years will be calculated, along with an exact 90% confidence interval, both two-sided as well as a lower 90% confidence limit. The number of patients alive and progression-free at 2 and 3 years will be used to address the primary hypothesis as indicated in section 10.2 above. In addition, a Kaplan-Meier curve will be calculated to obtain the actuarial estimate of two-year progression-free survival.

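### The 3-year PFS population is defined both as at least one dose (6.1) and as at least one complete cycle with replacement (Study Summary, 3.0), and the success rule is stated only for 36 patients

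*Combined protocol and SAP*

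**What the plan says.** Section 6.1 sets the population for the primary endpoint: "Any patient who receives at least one dose of study treatment will be evaluable for this endpoint".

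The Sample Size row of the Study Summary says "patients who receive < 1 complete cycle of therapy will not be considered evaluable for efficacy endpoints and will be replaced" and expects this to affect three or fewer subjects. Section 3.0 carries the same meaning into the accrual target: 36 evaluable "subjects will be needed for this trial (defined as having received" at least one complete cycle). Section 6.2.1, when defining who is evaluable for toxicity, still refers to dosed patients "including those who are replaced for efficacy endpoints".

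The sample size statement, in the Study Summary and again in 10.2, is "Based upon these parameters, our sample size will be 36 evaluable patients". The regimen is judged ineffective "if 25 or fewer patients are alive and without progression from among all 36 evaluable patients accrued"; 26 or more is success. No cut-off is given for any other number. Section 10.3.1 refers the primary hypothesis back to 10.2 and names no population. It does plan an exact lower 90% confidence limit, but does not make it the decision criterion.

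Sections 6.2.2 and 10.3.2 apply a one-cycle rule to PR-to-CR conversion ("Only patients who had a PR at the time of registration and who complete" at least one cycle). That rule is specific to its endpoint and is not in dispute.

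**The concern.** PFS is an efficacy endpoint, so the Summary removes from it the same patients whom 6.1 keeps. Both statements are in current operative text. The history of changes in Appendix IV records that 6.1 was moved to the one-dose population because an intention-to-treat design was intended. It is cited here only for intent; the conflict exists without it.

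Two analysts who follow the protocol faithfully can build different primary analysis sets. A patient who progresses or dies in cycle 1 is a PFS event under 6.1 and absent under the Summary. In a single-arm trial decided by a count, one patient can change the conclusion. If the choice is still open when outcomes are known, it can be made with knowledge of who progressed.

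**Working it through.** **Inputs.** From 10.2: null 60%, alternative 80%, type I error 10%, power 90%, N = 36, success at 26 or more. From the Study Summary: three or fewer patients replaced. The documents give no PFS for patients who stop in cycle 1, so two assumptions are shown: the stopper certainly fails, or has the same PFS as everyone else. All probabilities are exact binomial.

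**1. The plan's own figure.** P(X ≥ 26 | 36, 0.6) = 0.0904 and P(X ≥ 26 | 36, 0.8) = 0.9111. The smallest n with alpha ≤ 0.10 and power ≥ 0.90 is 36, with cut-off 26. The design reproduces.

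**2. Three ways to read the text when someone stops in cycle 1.**
- Summary and 3.0 alone: the stopper is dropped and replaced; 36 one-cycle patients; 26/36 applies.
- 6.1 alone: nobody dosed is replaced for PFS; 36 dosed patients; 26/36 applies.
- Accrual by the Summary and 3.0, analysis by 6.1: the stopper is replaced and still counted; N = 37, 38 or 39; no cut-off stated.

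**3. Summary against 6.1 alone, one stopper.** The two sets share 35 patients; one has the stopper, the other an independent replacement. They disagree only if exactly 25 of the 35 succeed and the stopper and replacement differ. P(25 of 35) is 0.0547, 0.1454 and 0.0710 at true PFS 60%, 70% and 80%.
- Stopper fails: multiply by p. 0.0547 × 0.6 = 3.3%; 0.1454 × 0.7 = 10.2%; 0.0710 × 0.8 = 5.7%.
- Stopper has the same PFS: multiply by 2p(1 − p), that is 0.48, 0.42 and 0.32. This gives 2.6%, 6.1% and 2.3%.

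**4. Summary against all dosed patients, one stopper.** The plan has no cut-off for 37. The smallest with alpha ≤ 10% is 27, derived here. The readings disagree only if exactly 26 of the other 36 succeed and the stopper does not. P(26 of 36) is 0.0455, 0.1409 and 0.0787.
- Stopper fails: 4.5%, 14.1%, 7.9%.
- Same PFS, multiply by (1 − p): 1.8%, 4.2%, 1.6%.

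**5. One rule for any N.** Clopper-Pearson one-sided lower 90% limits at the smallest cut-off with alpha ≤ 10%, and at one success fewer:

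| N | Cut-off | Limit at cut-off | Limit at one fewer | Alpha at 60% | Power at 80% |
|---|---|---|---|---|---|
| 36 | 26 | 0.6047 | 0.5756 | 9.0% | 91.1% |
| 37 | 27 | 0.6145 | 0.5861 | 7.2% | 89.5% |
| 38 | 28 | 0.6238 | 0.5961 | 5.7% | 87.8% |
| 39 | 28 | 0.6056 | 0.5787 | 8.8% | 92.6% |

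Requiring the limit to exceed 60% gives back 26/36 exactly and supplies the other cut-offs.

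**6. Power if replaced stoppers are counted and all fail.** With 80% PFS in the other 36, power is P(X ≥ 27 | 36, 0.8) = 83.2% for one stopper, and P(X ≥ 28 | 36, 0.8) = 71.6% for two or three.

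**The case against.** The strongest reply is that each definition, taken alone, has a success rule. The Summary replaces patients because it does not count them; 6.1 counts them and then has no reason to replace them. Either way the set is 36 and 26 decides. An N of 37 to 39 needs a mixture of the two. This stands, and it rules out saying that the plan lacks a success criterion. It does not remove the problem: the two sets of 36 contain different patients, and the mixture is a natural result of the accrual target in 3.0 differing from the population in 6.1.

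A second reply is that the plan already holds most of the remedy. Section 10.3.1 plans the exact lower 90% limit, and at N = 36 that limit exceeds 60% exactly when the count reaches 26. This is also right; what is missing is the sentence that makes it the decision rule.

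Third, early stoppers may be less well observed. Section 4.7 follows them for survival endpoints, including date of progression, up to 4 years from first dose. The schedule in 5.0, however, marks no CT or MRI at end of treatment or in follow-up. Its footnotes leave end-of-treatment imaging to clinical judgement and require no labs or examination in follow-up. Counting these patients is possible, but their progression may be found later or less reliably.

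Finally, few such patients are expected, and with one of ordinary prognosis the disagreement is only 1.6% to 6.1%. That limits the size of the problem, but not the need to name one population.

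**Conclusion.** The point holds. The current text gives two incompatible populations for the primary endpoint and a cut-off for one sample size only. The effect is zero if nobody stops in cycle 1. With one stopper and true PFS of 60%, 70% or 80%, the Summary and 6.1 taken alone disagree in 3.3%, 10.2% or 5.7% of trials if the stopper fails, and in 2.6%, 6.1% or 2.3% if the stopper has the same PFS as the others. Against an all-dosed analysis at 27/37 the figures are 4.5%, 14.1% or 7.9%, and 1.8%, 4.2% or 1.6%; these depend on a cut-off derived here. All rest on assumed outcomes for early stoppers and on independence between patients.

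Three stronger conclusions are not supported:
- **That the sample size is wrong.** The 26/36 design meets its stated error rates.
- **That type I error is inflated.** Keeping 26 as the cut-off at N = 37, 38 or 39 would give alpha of 13.3%, 18.6% or 24.8%, but nowhere does the plan say to do so. Dropping and replacing stoppers whose PFS is also 60% leaves alpha at 9.0%.
- **That the conclusion is likely to reverse.** With two or three stoppers who all fail, disagreement with the derived cut-offs reaches 26.3% at a true PFS of 70%, but nothing in the documents says that early stoppers all fail.

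**What to change.** For the primary endpoint only, use the population of 6.1 (at least one dose) in the Study Summary, 3.0, 6.2.1 and 10.2. Leave the one-cycle rule for PR-to-CR conversion in 6.2.2 and 10.3.2 as it is.

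In 10.2, and in its repetition in the Study Summary, state before outcomes are reviewed that success means the exact one-sided lower 90% limit for the 3-year progression-free proportion, already planned in 10.3.1, exceeds 60%. List the equivalent counts: at least 26/36, 27/37, 28/38 or 28/39. This covers both 36 dosed patients and a larger number if some have been replaced. Report the one-cycle set as a sensitivity analysis.

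The cost is wording and some power. If all dosed patients have 80% PFS, power falls just below 90% at N = 37 (89.5%) and N = 38 (87.8%). It falls to 83.2% with one replaced stopper, or 71.6% with two or three, if they are counted and all fail. The report should also state that progression in early stoppers was ascertained without scheduled imaging. How to count patients of unknown 3-year status, and the mention of 2-year counts in 10.3.1, are separate matters that this change does not settle.

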### 6.2 Secondary Endpoints

#### 6.2.1 Toxicity

All patients who receive at least one dose of ibrutinib will be evaluable for toxicity (including those who are replaced for efficacy endpoints). The study will use the CTCAE version 4.03 (see appendices for link) for reporting of adverse events. The occurrence and severity of each will be recorded.

After the study has been opened for 18 months, patients will be evaluated for an interim safety analysis. The PI along with the Northwestern Lymphoproliferative Disorders disease team and Quality Assurance will assess data to ensure there are no unexpected safety signals that have been observed at this time. See section 10.3.4 for details on the safety analysis.

#### 6.2.2 Rate of conversion from PR to CR

Progression will be evaluated using Cheson 2007 criteria (Revised Response Criteria for Malignant Lymphoma, modified). Patients must have already achieved either PR or CR during induction chemotherapy prior to enrolling in this study. Patients with measurable disease at time of enrollment will have it followed with imaging. Only patients who had a PR at the time of registration and who complete  $\geq 1$  complete cycle of ibrutinib maintenance therapy will be evaluable for this endpoint. Please refer to appendices for a summary of Cheson criteria.

#### 6.2.3 Median overall survival at 4 years

Overall survival (OS) will be defined as the duration of time from start of treatment up to 4 years from the start of study treatment.

### 6.3 Exploratory Endpoints

We will collect archived tissue (FFPE slides) from a prior biopsy as well as peripheral whole blood samples from all patients. Peripheral blood samples will be collected at baseline, after 1 month of treatment, 6 months of treatment, and approximately 18-24 months post-first dose. MRD analysis will be conducted using PCR methods and results over time will be compared and correlated with PFS and OS. Please see section 9.0 for details.

## 7.0 ADVERSE EVENTS

This study will be conducted in compliance with the Data Safety Monitoring Plan (DSMP) of the Robert H. Lurie Comprehensive Cancer Center of Northwestern University (please refer to the protocol page in NOTIS for additional information). The level of risk attributed to this study requires High Intensity Monitoring, as outlined in the DSMP. In addition, the study will abide by all safety reporting regulations, as set forth in the Code of Federal Regulations and as required by the NCI AdEERS Reporting Guidelines.

This study has been designated as an interventional study. As such, all adverse events and special situations, including pregnancies and product quality complaints, will be reported from the time a subject has signed and dated an Informed Consent Form (ICF) until 30 days after the last documented use of the product under the study within the study. Adverse events that result in treatment discontinuation will be followed until resolution or until the patient starts subsequent therapy, whichever comes first.

For the purposes of this study, the Janssen medicinal product is: Ibrutinib (Imbruvica)

### 7.1 Adverse Event Monitoring

Adverse event data collection and reporting, which are required as part of every clinical trial, are done to ensure the safety of subjects enrolled in the studies as well as those who will enroll in future studies using similar agents.

Adverse events are reported in a routine manner at scheduled times during a trial. Additionally, certain adverse events must be reported in an expedited manner to allow for optimal monitoring of patient safety and care. All adverse events (regardless of severity) will be recorded in the appropriate eCRF throughout the study.

All patients experiencing an adverse event, regardless of its relationship to study drug, will be monitored until:

- the adverse event resolves or the symptoms or signs that constitute the adverse event return to baseline;
- any abnormal laboratory values have returned to baseline;
- there is a satisfactory explanation other than the study drug for the changes observed; or
- death occurs.

## 7.2 Definitions & Descriptions

### 7.2.1 Adverse event (AE)

An adverse event (AE) is any untoward medical occurrence in a patient receiving study treatment and which does not necessarily have a causal relationship with this treatment. An AE can therefore be any unfavorable and unintended sign (including an abnormal laboratory finding), symptom, or disease temporally associated with the use of an experimental intervention, whether or not related to the intervention.

Recording of AEs should be done in a concise manner using standard, acceptable medical terms. In general, AEs are not procedures or measurements, but should reflect the *reason* for the procedure or the diagnosis based on the abnormal measurement. Preexisting conditions

that worsen in severity or frequency during the study should also be recorded (a preexisting condition that does not worsen is not an AE). Further, a procedure or surgery is not an AE; rather, the event *leading to* the procedure or surgery is considered an AE.

If a specific medical diagnosis has been made, that diagnosis or syndrome should be recorded as the AE whenever possible. However, a complete description of the signs, symptoms and investigations which led to the diagnosis should be provided. For example, if clinically significant elevations of liver function tests are known to be secondary to hepatitis, "hepatitis" and not "elevated liver function tests" should be recorded. If the cause is not known, the abnormal test or finding should be recorded as an AE, using appropriate medical terminology (e.g/ thrombocytopenia, peripheral edema, QT prolongation).

